3.0 Study Design

3.1 Study Summary

[figure not shown]
This will be a phase III, multicenter, open-label study to evaluate the relative efficacy of pegylated interferon and ribavirin in African American versus Caucasian patients with chronic hepatitis C and genotype 1. Participating centers and Principal Investigators in the study are shown in Table 1. A total of 200 African American and 200 Caucasian patients will be enrolled at 8 medical institutions. All patients will be genotype 1 and have quantifiable (600 IU/ml) HCV RNA. After careful evaluation, all patients will receive the same regimen of peginterferon alfa-2a and ribavirin (1000/1200 mg). Peginterferon will be administered once weekly by subcutaneous injection and ribavirin will be administered orally twice daily. After 24 weeks of treatment, HCV RNA will be tested by qualitative PCR in duplicate to identify responders (undetectable serum HCV RNA) and non-responders (HCV RNA positive in duplicate). Responders will continue on therapy for another 24 weeks whereas treatment for non-responders will cease. Follow-up will continue for 48 weeks after completing therapy for responders and 24 weeks after completing therapy for nonresponders. Patients whose qualitative PCR results are indeterminate or discordant will follow the protocol for responders.

Sustained virological response (SVR, defined above) will be measured 24 weeks following completion of therapy. The durability of SVR will be measured at the end of the follow-up period, 48 weeks after discontinuing therapy.

Location of Participating Centers										
Institution Location Principal Investigator Type of Center										
Beth Israel Deaconess Medical Center	Boston, MA	[name]	Clinical Center							
New York-Presbyterian Medical Center	New York City, NY	[name] MD, MPH	Clinical Center							
University of California, San Francisco	San Francisco, CA	[name], MPH	Clinical Center							
Rush University	Chicago, IL	[name]	Clinical Center							
University of [name]	[name]	Clinical Center							
University of Miami	Miami, FL	[name]	Clinical Center							
University of Michigan	Ann Arbor, MI	[name]	Clinical Center							
University of North Carolina	Chapel Hill, NC	[name]	Clinical Center							
University of Pittsburgh	Pittsburgh, PA	[name]	Data Coordinating Center							

Table 1 Location of Participating Centers				
Location of Participating Centers				

A schematic of the study design is shown in **Figure 1**. The required study visits and evaluations that will be performed at various time points are shown in subsequent tables.

3.2 Study Population

Definition of Race

For the purposes of classifying race, we will use self-identification. All participants must have been born in the United States. Racial and ethnic (Hispanic, non-Hispanic by self-identification) data will be collected in a self-report questionnaire completed by the patients (Appendix 1). A research coordinator will be available to answer questions about the form.

3.3 Entry Criteria

Inclusion Criteria

To be eligible for this trial, patients must meet the following inclusion criteria:

- Males or females; age between 18 and 70 years at screening
- Identify themselves as being Black/African American or White/Caucasian only, but not both
- Born in the United States (50 states)
- Serum HCV RNA above quantifiable level of detection (600 IU) (Roche HCV Monitor)
- HCV genotype 1 (alone or in combination with other genotypes)
- Liver biopsy obtained within 18 calendar months prior to screening. Patients with cirrhosis (Ishak Score 5-6) as assessed by [name] using a biopsy performed more than 18 months before screening will not need to undergo repeat biopsy.
- Patients with AFP above 100ng/ml and less than 500ng/ml, or patients with cirrhosis or transition to cirrhosis (Ishak score 3-6), must have an abdominal ultrasound, CT scan or MRI scan without evidence of hepatocellular carcinoma (within 8 months of treatment initiation), and the AFP level is shown to be stable (within 50ng/ml) or decreasing on repeat testing before enrollment.

 Negative urine pregnancy test (for women of childbearing potential) documented within the 24-hour period prior to the first dose of test drug. Additionally, all fertile male patients, male patients with female partners of childbearing age, and females of childbearing potential must be using two reliable forms of effective contraception during the study (while on drug and for 24 weeks following end of therapy).

Exclusion Criteria

Patients with any of the following will not be eligible for participation:

- Previous treatment with interferon or ribavirin
- Positive test at screening for anti-HIV
- Positive test for HBsAg done within the past 12 months
- Alcohol consumption of more than two drinks or equivalent (>20 grams) per day. Patients who consumed more than this in the past must have maintained a level of 20 grams or less per day of alcohol consumption for at least six months prior to screening.
- History of other chronic liver disease, including metabolic diseases, documented by appropriate test(s)
- Women with ongoing pregnancy or breast-feeding, or contemplating pregnancy
- Male partners of women who are pregnant or contemplating pregnancy
- Neutrophil count <1000 cells/mm³, Hgb <11 g/dl in women or 12 g/dl in men, or platelet count <75,000 cells/mm³. Any patient with a baseline increased risk for anemia (e.g. thalassemia, spherocytosis, history of GI bleeding) or for whom anemia would be medically problematic.
- Serum creatinine level >1.5 times the upper limit of normal at screening or CrCl < 75cc/min, or currently on dialysis
- Evidence of alcohol or drug abuse within 6 months prior to screening
- Any current (within past 6 months) severe psychiatric disorder such as depression, schizophrenia, bipolar illness, obsessive-compulsive disorder, severe anxiety, or personality disorder
- A prior suicide attempt, hospitalization for psychiatric disease, or a period of disability or impairment due to a psychiatric disease within the past 5 years. Patients whose psychiatric disease is controlled by medication and deemed psychologically stable by the investigator will be eligible for participation.
- History of immunologically mediated disease (e.g., inflammatory bowel disease, idiopathic thrombocytopenic purpura, lupus erythematosus, autoimmune hemolytic anemia, severe psoriasis, rheumatoid arthritis)
- History or other evidence of decompensated liver disease defined as any of the following: serum albumin <3 g/dl, direct bilirubin > 1.0 mg/dl, or PT/INR > 1.5 times normal, history or presence of ascites or encephalopathy, or bleeding from esophageal varices, or current jaundice
- History of cardiovascular or coronary artery disease, if, in the judgment of the investigator, an acute decrease in hemoglobin by up to 4 g/dl (as may be seen with ribavirin therapy) would not be welltolerated
- History of a severe seizure disorder or patient has had seizures despite anticonvulsant therapy in the previous 2 years
- History of solid organ or bone marrow transplantation
- History of thyroid disease poorly controlled on prescribed medications
- History or other evidence of retinopathy on physical examination (history or fundoscopic evidence of retinal hemorrhage, retinal artery obstruction, retinal vein obstruction, cotton-wool spots)
- Chronic use of oral steroids
- Inability or unwillingness to provide informed consent or abide by the study protocol
- History or other evidence of severe illness or any other conditions that would make the patient, in the opinion of the investigator, unsuitable for the study

3.4 Study Treatment

All participants will receive identical treatment regimens consisting of peginterferon alfa-2a in pre-filled syringes in a dose of 180 μ g administered once every 7 days by subcutaneous injection and ribavirin tablets administered twice daily at a dose of 1000 or 1200 mg/day (for body weights of < or \geq 75 kg, respectively). The treatment period will be for 48 weeks except for those defined as "non-responders" to therapy (defined below) or in those with early discontinuation (see below).

Peginterferon has undergone extensive clinical evaluation and is in the process of licensure review by the FDA. An IND (BB-IND10355) has been filed for the current trial. Details of these agents are available in the attached investigators brochure. (Appendix 2)

3.4.1 Dose Adjustment Guidelines

Specific dose adjustment guidelines for peginterferon are provided in the tables below for treatment-related neutropenia, thrombocytopenia, and anemia. For other adverse effects considered to be possibly related to peginterferon, including laboratory abnormalities, adverse events, and vital signs changes, investigators should utilize the "General Dose Reduction Guidelines" (Section 3.4.2) below. When practical, abnormal laboratory results should be confirmed as soon as possible following notification of the investigator. If appropriate, downward adjustments in one level increments (see below) should be considered. The lowest dose of peginterferon that should be administered is 45 μ g. It should be kept in mind that whereas these guidelines should be generally followed to promote consistency across centers, other responses by an investigator may be more appropriate in some circumstances. For laboratory and vital signs abnormalities, "severe" is defined as any value requiring intervention, further work-up, or more frequent follow-up.

3.4.2 General Dose Reduction Guidelines

The dose of study medications may be decreased due to adverse events or laboratory abnormalities. Dose reduction for peginterferon will be accomplished in graduated steps: Level 1 decrease from 180 μ g to 135 μ g; level 2 decrease from 135 μ g to 90 μ g; level 3 decrease from 90 μ g to 45 μ g.

Peginterferon vials of 90 μ g will be used for dose reduction requiring 90 μ g or 45 μ g. These will not be pre-filled syringes, and clinical center personnel will be instructed on the use of these vials.

Neutrophils (cells/mm3)	Downward Dose Adjustment
< 500	Decrease dose stepwise by one level
< 250	Stop drug
Platelet Count (cells/mm3)	Downward Dose Adjustment

 Table 2

 Peginterferon Dose Adjustments for Low Absolute Neutrophil and Platelet Counts

Platelet Count (cells/mm3)	Downward Dose Adjustment
≥40,000	None
25,000 to < 40,000	Decrease dose stepwise by one level
< 25,000	Stop drug
_0,000	

For subjects who require a downward dose adjustment for neutropenia or thrombocytopenia, laboratory values should be repeated, if practical, prior to the next dose of peginterferon to confirm the result and dictate the course of action. Subjects who remain with a neutrophil count below 500 (but above 250) or a platelet count below 40,000 (but above 25,000) should receive stepwise dose reductions until levels of neutrophils and platelets are \geq 500 or 40,000 cells/mm3, respectively, or until a dose of 45 µg of peginterferon is reached.

	Ribavirin Dose Adjustment for Anemia									
Hemoglobin (g/dL)	Initial dose	Reduced dose								
≤ 10 − 8.5	1000 mg q.d.	600 mg q.d.								
	1200 mg q.d.	800 mg q.d.								
< 8.5	Regardless of dose	Discontinue permanently								

Table 3 Ribavirin Dose Adjustment for Anemia

If laboratory abnormalities improve or resolve, the dose of peginterferon or ribavirin may be increased back to original dosing at the discretion of investigators with continued close monitoring. However, study participants must maintain blood counts consistent with the above schedule in order to remain on the original dose. If dose reduction is required for 4 consecutive weeks, reduced dose should be continued for the remainder of the study. Dose reduction for non-laboratory-related adverse events will be based upon severity ratings in accordance with modified WHO criteria (Appendix 3). For grade 1 toxicity, no dose reduction is needed. For toxicity grade 2 that persists over two consecutive safety visits and is not responsive to adjunctive symptomatic management, a level 1 dose decrease of peginterferon and/or a decrease in ribavirin may occur. For toxicity grade 3 not responsive to adjunctive measures, a level 1 dose decrease of peginterferon and/or a decrease in ribavirin will occur. Stepwise reduction will continue as noted above until symptoms abate or until the lowest allowable dose of peginterferon (45µg) is reached. Patients with grade 3 toxicity should be followed closely, possibly at more frequent intervals or via telephone contact to monitor in between regularly scheduled safety visits. If symptoms improve, return to previous dosing is allowed at the discretion of the investigator. For grade 4 toxicities, treatment will be discontinued. It should be noted that certain toxicities carry different levels of significance for each patient and therefore, the investigator should use these as guidelines only, within the context of clinical judgment.

For non-hematologic adverse events, ribavirin dose reduction will be defined as follows: Level 1: decrease initial daily dose by 200mg (1200mg to 1000 mg or 1000mg to 800mg) Level 2: decrease an additional 200 mg/day (1000mg to 800mg or 800 mg to 600mg) Level 3: decrease an additional 200 mg/day (800 mg to 600 mg or 600mg to 400mg)

If adverse events improve, ribavirin may be increased to initial dosage at the discretion of the investigator provided that continued close monitoring is maintained. If adverse events continue at the same level of intensity despite maximal dose reduction, ribavirin may be discontinued at the discretion of the investigator.

Guidelines for controlling hepatic adverse events such as ALT flares, and abnormal total bilirubin and alkaline phosphatase are provided in Appendix 1.

Growth factors may not be used to maintain platelet counts, WBC, or hemoglobin levels.

3.4.3 Safety Measurements

Laboratory evaluations: Participants will undergo laboratory tests according to the time and event schedule to monitor for medication toxicities.

Adverse event monitoring: Participants will be queried by study personnel at each study visit about the incidence of adverse events. These will be documented in the study record and classified according to onset date, severity, relationship to study medication, action taken, and outcome. Serious adverse events will be reported to appropriate regulatory authorities (e.g., FDA), in addition to the Data Safety and Monitoring Board as described below, in a timely fashion.

Pregnancy: Women of child-bearing potential will have a urine pregnancy test performed within 24 hours of the first administration of study drugs, monthly for the duration of therapy, and at months 1, 3, and 6 following completion of therapy.

3.4.4 Depression Management Guidelines

Mood disorders (i.e., depression and anxiety) are common and problematic side effects of peginterferon. Mood disorders may develop during the first few months of treatment or later during therapy. Mood disorders can develop in individuals without a prior psychiatric history and present with subtle signs and symptoms such as fatigue, withdrawn behavior, poor appetite, irritability, or sleep disturbance. Although peginterferon dose reduction and anti-depressant medications have proven useful, severe and life-threatening neuropsychiatric toxicity including attempted and completed suicide have been reported. Therefore, a heightened awareness of depression and its potential impact on patient safety and compliance is necessary when prescribing peginterferon.

Detection of Depression

A local collaborative mental health professional (i.e. psychiatrist/ psychologist) will provide consultation and treatment for patients during screening and treatment. At each scheduled study visit, the patient will be assessed by the study coordinator for side effects, adverse events, and medication tolerance. At screen 1, baseline, weeks 4, 8, 12, 16, 20, 24, 28, 32, 36, 40, 44, and 48, and follow-up weeks 4, 12, 24, and 48, three questions regarding mood status will be asked.

- 1. Since your last visit, have you felt depressed, sad or blue most of the time? Yes or No
- 2. Since your last visit, have you often felt helpless about the future? Yes or No
- 3. Since your last visit, have you had thoughts about harming or killing yourself or others? Yes or No

If the patient responds Yes to any of the questions, the investigator will be informed and a management plan will be instituted after review of the patient.

Management of depression

Patients who answer affirmatively to any of the depression screening questions, appear to be clinically depressed, or suffering from other psychiatric side effects will be reviewed by the investigator. Recommended management steps include:

- 1. Reassurance with careful monitoring and close follow-up every 2-4 weeks for patients with minimal or mild symptoms.
- 2. Anti-depressant medications or referral to a mental health provider for patients with mild to moderate depressive symptoms.
- 3. Stepwise peginterferon dose reduction may be required as well as consultation with the mental health provider for patients with moderate to severe depressive symptoms (see dose adjustment guidelines).
- 4. For patients with severe depression or depression that is worsening despite peginterferon dose reduction, anti-depressants, or referral to a mental health professional, the study medications should be discontinued. These patients should be rapidly referred to the local collaborative mental health provider for further assessment and treatment.
- 5. Any patient who develops recurrent suicidal ideation, a suicide plan and/or makes a suicide attempt should have both peginterferon and ribavirin immediately discontinued and should be referred to the local mental health provider for further management.

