4.3 Baseline Visit (Day 0): Once the patient has completed the two screening visits and has been confirmed to be eligible, he/she will return for additional laboratory studies and comprehensive instruction in self-injection techniques by study personnel. These three visits, screening 1, screening 2, and baseline (day 0) will occur within 56 days.

Interim Medical History	
CBC/Differential	
Chemistry	ALT, AST, AlkPO4, total and direct bilirubin, fasting triglycerides, glucose, insulin
Serum Storage	Serum 3ml
Viral Genetics	
Patient Genetics	
Viral Kinetics	HCV RNA quantitative
Pharmacokinetics	Peginterferon alfa-2a levels, 2',5'-OAS serum activity
Interferon Signaling	
Pregnancy Test	Urine
Adherence MATI	
Medication Education	Self-injection techniques (including video), use of MEMS caps, adherence materials
Study Medication Administration	Supervised by research coordinator

Table 6 Baseline (Day 0) visit

4.4 Treatment Period: Pegylated interferon will be administered as a weekly subcutaneous injection and ribavirin will be administered as tablets twice daily. Treatment will be continued for 48 weeks (except in the absence of virological response as defined below). During the treatment period, participants will return for safety and efficacy evaluations at weeks 1, 2, 4, 6 (safety labs only), and 8, and then monthly until treatment is completed.

Efficacy assessment at week 24 will determine if participants are eligible to continue the full 48 weeks of treatment. Participants who have a positive qualitative test result, in duplicate, will be discontinued from study medication at week 24. These participants will then enter the follow-up period and be followed for an additional 24 weeks (post-treatment weeks 4, 12, 24). If they begin other antiviral therapy, they will be discontinued from follow-up.

Interim Medical History	
Symptom-directed Physical Exam	Vital signs and weight at each visit; physical exam every 3 months or as needed
Adverse Event Assessment	
Concurrent Medication Assessment	
CBC/Differential	Each visit (except days 1 and 2)
Chemistry	Each visit except week 1; ALT, AST, AlkPO4, total and direct bilirubin, albumin, uric acid, BUN, creatinine, glucose. Fasting triglycerides, glucose, and insulin at week 24, and week 48 for responders only.
Pregnancy Test	Urine, each visit (except days 1and 2)
TSH	Weeks 12, 24, 36, 48
PT/PTT	Weeks 24 and 48

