Viral Genetics	Days 1, 2, 7, 14, 28, and weeks 8, 12, and 24. For responders, at end of treatment (48 weeks)
Viral Kinetics	Days 1, 2, 7, 14, 28, and weeks 8, 12, 24, and 36. For responders, at end of treatment (48 weeks)
Pharmacokinetics (PEG-IFN alfa-2a levels 2',5'- OAS serum activity)	Days 1, 2, 7, 14, 28, and weeks 8, 12, and 24. For responders, at end of treatment (48 weeks)
Serum Storage	Each visit (except weeks 6, 16, 20, 28, 32, 40, 44)
Interferon Signaling	Days 1, 2, 7, 14, 28

Table 7Safety and Efficacy Visits

Immunology (CD4/CD8)	Weeks 8, 24, and end of treatment (week 48 for responders), or at early termination visit
CES_D*	Weeks 4, 12, 24, 48
Symptom Assessment	Each visit (except days 1 and 2)
Questionnaire*	
Brief MATI	Weeks 4, 12, 20, 28, 36
Gratitude Letter	Weeks 12, 36
Telephone Call	Week 24-26 (pending viral studies)
MEMS Use Questionnaire*	Weeks 4, 8, 12, 16, 20, 24, 28, 32, 36, 40, 44, 48
Adherence Questionnaire*	Weeks 4, 12, 24, 36, 48
Social Support and Self-	Week 24
efficacy Questionnaire*	
Sexual Function	Weeks 4, 12, 24, 48
Questionnaire*	
Adherence Videos	Weeks 1, 4, 12, 24, 36
Data Collection from Electronic	Weeks 4, 8, 12, 16, 20, 24, 28, 32, 36, 40, 44, 48
Monitors	

*Also assessed at the time of early termination for patients who discontinue prior to Week 24.

4.5 Follow-up Period: Participants will be followed for an additional 48 weeks following end of treatment. Participants who responded to therapy at week 24 will be treated for 48 weeks. They will return for post-treatment follow-up visits at follow-up weeks 4, 12, 24, 36, and 48. Non-responders will be followed for 24 weeks only. During these visits, participants will be evaluated for resolution of adverse events and laboratory studies will be drawn to measure efficacy. Participants will be contacted by telephone on one occasion between follow-up visits in order to foster continuity and encourage adherence with study follow-up.

Follow-up visit Procedures						
Interim Medical History						
Symptom-directed Physical	Vital signs and weight at each visit; physical exam at weeks 12, 24,					
Exam	and 48, and as needed					
Adverse Event Assessment						
Concurrent Medication						
Assessment						
CBC/Differential	Each visit					
Chemistry	Each visit: ALT, AST, AlkPO4, direct bilirubin					
	Follow-up weeks 12, 24, 48: albumin, uric acid, BUN, creatinine,					
	glucose					
	Follow-up week 24: fasting triglycerides, glucose, insulin					

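### The mood and self-harm questions look back only to the last visit but are not asked at every visit, leaving treatment weeks 0–2 and, for those followed to week 48, follow-up weeks 24–36 uncovered

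*Protocol*

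**What the plan says.** Section 3.4.4 of the protocol gives the wording of three mood items. All three refer to the time since the participant's last visit, and the third is the self-harm question: "Since your last visit, have you had thoughts about harming or killing yourself or others". They are listed at Screen 1, at baseline, every four weeks from week 4 to week 48, "and follow-up weeks 4, 12, 24, and 48, three questions regarding mood status will be asked".

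The visit schedule is denser than that. Section 4.4 states that "participants will return for safety and efficacy evaluations at weeks 1, 2, 4, 6 (safety labs only), and 8", then monthly, and Table 7 lists procedures on days 1 and 2. For week-24 responders, Section 4.5 says: "They will return for post-treatment follow-up visits at follow-up weeks 4, 12, 24, 36, and 48". For the others it says: "Non-responders will be followed for 24 weeks only". The items are not listed at days 1 and 2, at weeks 1, 2 and 6, or at follow-up week 36.

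On timing of risk, Section 3.4.4 says: "Mood disorders may develop during the first few months of treatment or later during therapy".

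**The concern.** A look-back to the last visit covers the whole study only if the question is asked at every visit. Wherever a visit passes without the items, the next asking reaches back to that visit and no further, and the time before it is never asked about.

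The third item is the only direct self-harm question whose wording the protocol shows. A participant who had such thoughts in week 1, and none after week 2, can truthfully answer no at week 4. That answer can affect management. Among the steps in Section 3.4.4, repeated suicidal thoughts require both drugs to be stopped at once. If a first episode falls in a gap, a second may look like the first.

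**Working it through.** The protocol gives no figure to reproduce. The check compares the two schedules. For each asking at time *a*, the literal window runs from the latest earlier scheduled visit to *a*. Any interval between visits that lies in no window is uncovered.

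**Inputs**
- Treatment visits (Section 4.4, Table 7): days 0, 1, 2, 7, 14, 28, 42 (labs only), 56, 84 and so on to 336.
- Items during treatment (Section 3.4.4): days 0, 28, 56, 84 and so on to 336.
- Follow-up visits for responders (Section 4.5): weeks 4, 12, 24, 36, 48.
- Items in follow-up (Section 3.4.4): weeks 4, 12, 24, 48.
- Length of treatment for responders and of their follow-up: 48 × 7 = 336 days each.

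**Windows and gaps**

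| Asking | Previous visit | Window | Left uncovered |
|---|---|---|---|
| Week 4 | Week 2 | Weeks 2–4 | Weeks 0–2 |
| Week 8, week 6 not counted as a visit | Week 4 | Weeks 4–8 | None |
| Week 8, week 6 counted as a visit | Week 6 | Weeks 6–8 | Weeks 4–6 |
| Weeks 12 to 48 | Four weeks earlier | Preceding 4 weeks | None |
| Follow-up weeks 4, 12, 24 | Preceding visit, where the items were also asked | Full interval | None |
| Follow-up week 48 | Follow-up week 36 | Follow-up weeks 36–48 | Follow-up weeks 24–36 |

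**Size**
- Treatment, week 6 not counted: 14 days. 14/56 = 25.0% of the first eight weeks; 14/336 = 4.2% of treatment.
- Treatment, week 6 counted: 14 + 14 = 28 days. 28/56 = 50.0%; 28/336 = 8.3%.
- Follow-up, participants followed to week 48: 12 × 7 = 84 days. 84/336 = 25.0%.
- Follow-up, non-responders and early discontinuers: no gap, because their follow-up is planned for 24 weeks and the items are asked at every visit in it.

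Two smaller points come from the same wording. Screen 1 has no earlier study visit to refer to. Screening visit 2 does not list the items, so the baseline asking reaches back only to that visit and misses the time since Screen 1. Unscheduled visits (Section 4.6) would also shorten the next window, since the items are not listed there; the percentages above count scheduled visits only.

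**The case against.** The strongest reply is that the gaps are watched by other means. Section 3.4.3 provides that "Participants will be queried by study personnel at each study visit about the incidence of adverse events". The symptom questionnaire is given at weeks 1 and 2 and at follow-up week 36, and the CES-D is scheduled at week 4. Section 3.4.4 does not wait for a yes: patients who "appear to be clinically depressed, or suffering from other psychiatric side effects will be reviewed by the investigator". A lost episode in weeks 0–2 would have to begin and end within 14 days, go unmentioned at the week 1 and week 2 enquiries, and escape staff notice. Coordinators and participants may not read the phrase so literally. The first two items ask about sustained states, and one resolved episode would lead to review, not to the mandatory stop. The protocol places mood disorders in the first months or later, without singling out the first two weeks. The percentages are shares of calendar time, not of risk, and the follow-up gap opens 24 weeks after the last dose.

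Most of this stands, and it limits the weight of the point. It does not close the gaps. None of the other instruments is shown to ask directly about self-harm; their wording is not in the protocol, so neither presence nor absence of such a question can be established. The first CES-D on treatment comes only at week 4, and the only follow-up CES-D is at follow-up week 24, the point where the follow-up gap opens. The recurrence criterion also gives a resolved first episode some bearing on later management.

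**Conclusion.** The point holds. Read literally, the items never cover treatment weeks 0–2 or, for participants followed to week 48, follow-up weeks 24–36. Weeks 4–6 are a third gap only if the labs-only return counts as a visit, which the protocol leaves open.

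The consequence is modest. An episode that persists past a gap is caught at the next asking, so what can be lost is a transient episode that no other route picks up. How many there would be cannot be derived from the protocol. The early gap matters more, because it falls on treatment and within the months in which the protocol expects mood disorders to appear; the follow-up gap carries lower risk. No endpoint or efficacy analysis is affected. The conclusion assumes that participants take the reference to the last visit at its word. It is worth correcting because the hole is in a suicidality screen and is cheap to close.

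**What to change.** - Reword all three items to begin *Since you were last asked these questions*, with the coordinator entering the date of the last asking. This also removes the effect of week 6, Screening visit 2 and unscheduled visits.
- At Screen 1, use a fixed look-back, for example the past 4 weeks.
- Ask the three items at the existing follow-up week 36 visit.
- Optionally, add a row for the items to the visit tables.

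The cost is a wording change on one form and three yes/no questions at one existing visit, with no new visit or sample. Recall at week 4 lengthens from 2 to 4 weeks (and at week 8 if week 6 counts as a visit), the same interval that already applies from week 12 to week 48. Events in weeks 0–2 would still be asked about only in retrospect, at week 4. Without the follow-up week 36 asking, the rewording would lengthen recall at follow-up week 48 from 12 to 24 weeks; with it, recall stays at 12.
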